#### **Day 1: Between 1 and <2 weeks after Study TV50717-CNS-30080 week 15 visit:**

To reduce patient burden and not collect duplicate information, after obtaining appropriate informed consent/assent, relevant data collected in Study TV50717-CNS-30080 will be used to provide corresponding data in this open-label study baseline/day 1 visit.

Day 1 assessments for Study TV50717-CNS-30081 that are identical to Study TV50717-CNS-30080 week 15/week 16 visit assessments, whichever is most current, **do not** need to be repeated, except for orthostatic pulse rate and blood pressure, electrocardiogram (ECG), beta-human chorionic gonadotropin ( $\beta$ -HCG) tests in urine, the site-administered scales, and the patient/caregiver-completed questionnaires, which need to be repeated at day 1.

Any scales/questionnaires administered at the week 16 visit for Study TV50717-CNS-30080 do not need to be repeated if the day 1 visit of Study TV50717-CNS-30081 is the same day as the week 16 visit Study TV50717-CNS-30080.

In addition, the following applies for day 1 baseline assessments for this study:

- clinically significant laboratory abnormalities identified at week 15 in Study TV50717-CNS-30080 are to be repeated at week 16 of the parent study for eligibility in Study TV50717-CNS-30081 and will serve as day 1 baseline values in this study. Any abnormalities which are listed in the inclusion/exclusion criteria must be discussed with the medical monitor prior to patient enrollment into the study.
- Urine drug screen is performed at week 16 in study TV50717-CNS-30080 and will serve as day 1 baseline values in this study.

- If the day 1 visit in Study TV50717-CNS-30081 is on the same day as the week 16 visit of Study TV50717-CNS-30080, the results of  $\beta$ -HCG tests in urine will be carried over from the week 16 visit. Otherwise, the  $\beta$  HCG tests in urine will be administered at day 1.
- weight is performed at week 16 in Study TV50717-CNS-30080 and height is performed at week 15 in study TV50717-CNS-30080; these assessments will serve as day 1 baseline values in this study.
- vital signs (respiratory rate and body temperature) are performed at week 16 in Study TV50717-CNS-30080. If the day 1 visit in Study TV50717-CNS-30081 is on the same day as the week 16 visit of Study TV50717-CNS-30080, these assessments will serve as day 1 baseline values in this study. Otherwise, these assessments will be performed at day 1.
- physical and neurological examinations are performed at week 15 (and week 16, if applicable) in Study TV50717-CNS-30080. The findings from the last assessment taken will serve as day 1 baseline values in this study.
- ECG is to be performed on day 1 of Study TV50717-CNS-30081 and will serve as day 1 baseline values in this study.
- medical and psychiatric history are to be assessed on day 1 of Study TV50717-CNS-30081 and will serve as day 1 baseline values in this study.
- COPM (an assessment included only in Study TV50717-CNS-30081) will also be performed at day 1.

At the investigator's discretion, abnormal findings can be discussed with the medical monitor.

**Day 1: Between 2 and  $\leq$ 4 weeks after Study TV50717-CNS-30080 week 15 visit:**

If, in the judgment of the investigator, the patient has *not* had any clinically significant change since the week 15 visit of Study TV50717-CNS-30080 in health, concomitant medications, clinical assessments, laboratories, ECGs, or non-medical interventions, the patient will undergo all day 1 assessments outlined in [Table 4](#), except hematology, chemistry, and urinalysis laboratories and urine drug screen, which can be carried over from Study TV50717-CNS-30080 week 15 or week 16 visit, whichever is more current.

If, in the judgment of the investigator, the patient has had a clinically significant change since the week 15 visit of Study TV50717-CNS-30080 in health, concomitant medications, clinical assessments, laboratories, ECGs, or non-medical interventions, the patient will undergo all screening procedures outlined in [Table 4](#). Patients who remain eligible for participation in the study will be asked to return for day 1 assessments.

Study drug will be dispensed at day 1 once all procedures and investigator-related assessments are completed and patient eligibility is confirmed.

For patients who enroll in the study between 2 and  $\leq$ 4 weeks after the Study TV50717-CNS-30080 week 15 visit, the investigator is required to consult with the medical monitor regarding eligibility prior to baseline/day 1. The patient's file should include all related correspondence with the medical monitor.

Because the patients from parent Study TV50717-CNS-30080 have discontinued TEV-50717 treatment for at least 1 week at completion of the parent study or received placebo in the parent study, all patients will undergo TEV-50717 dose titration (7 weeks) in this study in order to maintain the blind of the parent Study TV50717-CNS-30080. Patients will receive 6 mg of TEV-50717 ([Table 6](#)). This dose will be administered in the morning on days 2 and 3, followed by evening administration starting on day 3 for the remainder of the week (if body weight is  $\geq 40$  kg/88 lbs). TEV-50717 daily doses of 12 mg and higher will be administered as 2 divided equal doses, approximately 8 to 10 hours apart during the day. A minimum of 6 hours should elapse between doses.

The TEV-50717 tablets cannot be crushed or split, but should be swallowed whole; the TEV-50717 tablets should be taken with food (eg, a snack) and should not be taken on an empty stomach. The titration scheme and maximum dose will be determined by body weight at day 1 and CYP2D6 impairment status. Patients will be classified as CYP2D6 impaired if they are receiving a strong CYP2D6 inhibitor. Patients who are CYP2D6 impaired will have a dose cap in this study. Patients and their caregiver will interact weekly with the clinical research staff, either by telephone contact or in-clinic visits from week 1 through week 7 of the titration period, in order to evaluate safety and establish a dose of TEV-50717 that optimally reduces dyskinesia (as indicated by a reduction in the CGI-I) and is well tolerated (optimal dose). The telephone contacts to the patient will be supported by live video stream, without recording, to provide visual confirmation to the investigator of the verbal information provided by the patient or caregiver.

In-person (in-clinic) study visits will be scheduled at weeks 3 and 7, and telephone contacts will be scheduled for weeks 1, 2, 4, 5, and 6 in order to assess dyskinesia and adverse events.

The dose of TEV-50717 should be increased to reach a clinically meaningful reduction in dyskinesia, as indicated by a reduction in the CGI-I (see [Table 2](#)). The dose of TEV-50717 should not be increased further if either of the following occurs:

- the patient experiences a “clinically significant” adverse event (defined as an adverse event that is related to TEV-50717 and is either moderate or severe in intensity or meets the criteria for a serious adverse event), OR
- the maximum allowable dose is reached based on the patient’s weight and CYP2D6 impairment status at day 1. Patients will be classified as CYP2D6 impaired if they are receiving a strong CYP2D6 inhibitor.

Dose adjustments can be made up to and including the week 7 in-clinic visit. If an optimal dose is reached before the week 7 in-clinic visit, the dose of TEV-50717 should not be increased further, but the patient should continue on that dose for the remainder of the titration period. If a patient experiences a “clinically significant” adverse event attributable to TEV-50717, the investigator will first determine if a dose reduction (to the previous dose level) or suspension is necessary and possible. If the determination that a patient requires a dose reduction or suspension is made during a telephone contact, an unscheduled clinic visit should be conducted as soon as practicable thereafter.

Dose adjustments should be made based on all available information, including the patient and caregiver reports of adverse events and dyskinesia reduction, the clinical assessment of safety and efficacy by the investigator, and the information from rating scales.

During the maintenance period (week 8 to week 53), dose adjustments of TEV-50717 (upward or downward) may be made, if necessary, based on efficacy, safety, and/or tolerability considerations but not more often than every 5 days and only in increments of 6 mg up to the maximum allowed dose. In-person (in-clinic) study visits will be scheduled at weeks 14, 27, 40, and 53 for assessments of safety and efficacy, and telephone contacts will be scheduled for weeks 21, 33, and 46 in order to assess adverse events and dyskinesia.

All patients should continue their usual treatment regimen up to week 53 visit (ie, the last dose can be administered until visit completion, if applicable). No dosing will be given after the week 53 visit. All patients will discontinue TEV-50717 at the week 53 visit and will return 1 week later (week 54) for evaluation of safety. Patients will have a follow-up telephone contact for safety evaluation 1 week after the end of the washout period (ie, the period where no treatment is administered), which will be 2 weeks after their last dose of TEV-50717 (week 55).

**Method of Randomization and Blinding:** Not applicable. This is an open-label, single-arm study with no blinding.

**Investigational Medicinal Products: Dose, Pharmaceutical Form, Route of Administration, and Administration Rate:**

Test IMP is defined as TEV-50717 (deutetrabenazine, previously SD-809) in this study.

Test IMP will be administered as oral tablets at a starting dose of 6 mg once daily. Titration schemes based on body weight at day 1 are shown in [Table 2](#). The maximum daily dose is determined by body weight at day 1 and CYP2D6 impairment status ([Table 3](#)). Patients will be classified as CYP2D6 impaired if they are receiving a strong CYP2D6 inhibitor. If a patient experiences a “clinically significant” adverse event that is attributed to TEV-50717, the investigator will first determine if a dose reduction (to the previous dose level) or suspension is necessary and possible. At the end of the titration period, the patient’s initial dose will be established for the maintenance period. Dose adjustments of TEV-50717 (upward or downward) may be made during the maintenance period, if necessary, based on efficacy, safety, and/or tolerability considerations but not more often than every 5 days and only in increments of 6 mg up to the maximum allowed dose. As during titration, dose adjustments should be made based on all available information. The dose of TEV-50717 may be reduced or suspended if a patient experiences an adverse event or tolerability finding during the maintenance period and the investigator believes a dose reduction or suspension is warranted.

TEV-50717 oral tablets (test IMP) are 6, 9, and 12 mg, or other commercially available, dose strengths. Each dose strength will have a marking corresponding to the dose strength on the label. TEV-50717 will be supplied as 60-count tablets per bottle. Each dose strength will be a colored tablet with a marking of “SD” and the corresponding strength.

All IMP adjustments are made only after a remote or in-clinic visit; if the dose is escalated, the dose escalation will occur with the next morning’s dose.

TEV-50717 will be administered as follows:

- TEV-50717 cannot be crushed or split but should be swallowed whole; the TEV-50717 tablets should be taken with food (eg, a snack) and should not be taken on an empty stomach. Patients may be offered the optional use of a Medi+Straw®, which is a commercially available straw that can assist patients to overcome their swallowing difficulties.

- Dosing and titration will be based on body weight at the day 1 visit and CYP2D6 impairment status, as shown in [Table 2](#) and [Table 3](#), respectively.
- The starting dose is 6 mg in all patients. This dose will be administered in the morning on days 2 and 3, followed by evening administration starting on day 3 for the remainder of the week (if body weight is  $\geq 40$  kg/88 lbs). TEV-50717 daily doses of 12 mg and higher will be administered as 2 divided equal doses, approximately 8 to 10 hours apart during the day. A minimum of 6 hours should elapse between doses. If a patient misses a dose, and it is within 6 hours of the next dose, the missed dose should be skipped. If a patient is on the 6 mg once daily dose (12 kg to  $< 17$  kg; 26 lbs to  $< 37$  lbs) and experiences somnolence while taking the 6-mg dose in the morning, he/she may switch to taking it as an evening dose for the rest of the days up to day 14.
- Dose increases may not occur more frequently than every 5 days, except for patients  $\geq 40$  kg. For patients  $\geq 40$  kg, the first dose increase should be performed in an interval less than 5 days, only once, on day 3.
- During the week 3 visit, the investigator (or designee) will make sure the patient receives the evening dose to complete the week 3 dosing for that day. Refer to the pharmacy manual for further details.
- For any dose adjustment, the investigator or designee should confirm that patients have the bottle that contains the appropriate tablet strength and quantity to complete the recommended daily regimen.
- At an in-clinic visit, a dose reduction, if required, should be made to the previously tolerated dose level. **If more than 1 dose reduction is required for an adverse event, the medical monitor should be notified.**
- During the titration period, the dose of TEV-50717 should be adjusted according to [Table 2](#) to identify a dose level that optimally reduces dyskinesia (as determined by the investigator, as indicated by a reduction in the CGI-I) and is well tolerated. Dose adjustments should ONLY take place after a telephone or in-clinic visit.

**Test IMP:** TEV-50717 (deutetrabenazine, previously SD-809)

**Placebo IMP:** Not applicable

**Duration of Patient Participation and Maximal Exposure to IMP:** All participating patients are expected to participate in this study for its entire duration, which is 55 weeks. Patients will have a follow-up telephone contact to evaluate safety 1 week after the end of the washout period (2 weeks after their last dose of TEV-50717). Any patient that reaches the age of legal competence to give informed consent during the course of Study TV50717-CNS-30081 will need to be re-consented as an adult. When a patient is a minor advancing to the next age range (new assent available and patient is still considered a minor by local law), the patient may need to sign on new assent appropriate for that age in order to continue participation in the study (in accordance with local laws and regulations).

**Study Duration:** Approximately 55 weeks

**End of Study:** The end of the study TV50717-CNS-30081 is defined as the date of the week 55 follow-up telephone contact of the last participant.

**Plans for Treatment or Care after the Patient Has Ended Participation in the Study:** There are no plans to provide further treatment to patients upon completion of the study. An extension to the study may be considered on an annual basis.

**Inclusion Criteria:** Patients who meet the criteria below are eligible to be included in the study.

- a. Patient has completed week 16 of Study TV50717-CNS-30080.
- b. Patient weighs at least 12 kg (26 lbs) on day 1 of this study.
- c. Patient is able to swallow TEV-50717 whole.
- d. Patient and caregiver are willing to adhere to TEV-50717 regimen and comply with all study procedures.
- e. Patient is in good general health, as indicated by medical and psychiatric history and physical and neurological examination.
- f. In the investigator's opinion, the patient and/or caregiver has the ability to understand the nature of the study and its procedures, and the patient is expected to complete the study as designed.
- g. For a patient who is a minor, the parent(s)/legally acceptable representative(s) provides written informed consent, and the patient provides assent (in accordance with local regulations). Adult patients provide written informed consent (in accordance with local regulations), and the legally acceptable representative will sign, if needed.

In this study, eligible patients with dyskinetic cerebral palsy may have some degree of mental, motor, and/or communication (eg, speech, writing, etc.) limitations or disabilities. The patient may not be able to read the assent/consent form. Some patients may only be able to provide a limited assent/consent (for instance, by verbalizations or gestures). The investigator will determine the suitability of enrolling such patients in this study and will follow the local regulation to obtain the relevant consent/assent.

- h. A caregiver provides written informed consent after being assigned the role by an adult patient or if this role is delegated by the parent/legally acceptable representative of a patient who is a minor.
- i. Females who are postmenarchal or  $\geq 12$  years of age may be included only if they have a negative  $\beta$ -HCG test on day 1 or are sterile.
- j. Females who are postmenarchal or  $\geq 12$  years of age whose male partners are potentially fertile (ie, no vasectomy) must use highly effective birth control methods for the duration of the study (ie, starting day 1) and for 30 days after last dose of TEV-50717.

**Exclusion Criteria:** Patients will not be randomized/enrolled in this study if they meet any of the following criteria:

- a. Patient has clinically significant depression at screening or day 1 of this study.

- Note: Patients receiving antidepressant therapy may be enrolled if on a stable dose for at least 6 weeks before screening or day 1 (whichever comes first) and anticipated to remain stable (dose and frequency) within the study duration.
- b. Patient has a history of suicidal intent or related behaviors based on medical or psychiatric history or the C-SSRS at screening visit, if performed, or at the day 1 visit, as applicable according to the patient's age:
  - intent to act on suicidal ideation with a specific plan, irrespective of level of ambivalence, at the time of suicidal thought
  - suicidal preparatory acts or behavior
- c. Patient has a history of a previous actual, interrupted, or aborted suicide attempt based on medical or psychiatric history or the C-SSRS at screening visit, if performed, or at the day 1 visit, as applicable according to the patient's age.
- d. Patient has a first-degree relative who has completed suicide.
- e. Patient has received any of the following concomitant medications within the specified exclusionary windows from screening or day 1 (whichever comes first) of this study:
  - within 30 days: tetrabenazine or valbenazine
  - within 21 days: reserpine
  - within 14 days: levodopa, dopamine agonists, and monoamine oxidase inhibitors
- f. Patient has received treatment with stem cells, deep brain stimulation, transmagnetic stimulation, or transcranial direct current stimulation for treatment of abnormal movements or cerebral palsy since the week 15 visit of Study TV50717-CNS-30080, or the patient is not in a stable clinical condition.
- g. Patient had a surgical procedure since the week 15 visit of Study TV50717-CNS-30080 or is anticipated to have a surgical procedure during the study that, in the opinion of the investigator, makes the patient unsuitable for the study.
- h. Patient has a severe mental disability or an unstable or serious medical illness (eg, epilepsy) that, in the opinion of the investigator, could jeopardize or would compromise the patient's ability to participate in this study.
- i. Patient has a QT interval corrected for heart rate (QTc) using Fridericia's formula (QTcF) value  $>450$  msec on 12-lead ECG at screening or day 1 (whichever comes first) of this study.
- j. Patients with a history of torsade de pointes, congenital long QT syndrome, bradyarrhythmias, other cardiac arrhythmias, or uncompensated heart failure.
- k. Patient has evidence of hepatic impairment, as indicated by the following:
  - aspartate aminotransferase (AST) or alanine aminotransferase (ALT)  $>2.5 \times$  the upper limit of the normal range (ULN) at the week 15 or week 16 visit of Study TV50717-CNS-30080 or screening of this study, as applicable

- alkaline phosphatase (ALP) or total bilirubin (Tbil)  $>2\times$ ULN at the week 15 or week 16 visit of Study TV50717-CNS-30080 or screening of this study, as applicable
- Note: Patients with Gilbert's syndrome are eligible to participate if approved by the medical monitor.
- Note: Patients with abnormalities in 2 or more of AST, ALT, ALP, and Tbil parameters that do not meet the above laboratory criteria for exclusion based on hepatic impairment must be approved for enrollment by the medical monitor.

1. Patient has evidence of clinically significant renal impairment, indicated by a serum creatinine  $>1.5\times$ ULN at the week 15 or week 16 visit of Study TV50717-CNS-30080 or screening of this study, as applicable.
- m. Patient has a known allergy to any of the components of TEV-50717.
- n. Patient has participated in an investigational drug or device study other than Study TV50717-CNS-30080 and received IMP/intervention within 30 days or 5 drug half-lives of day 1 of this study, whichever is longer.
- o. Patient is pregnant or breastfeeding.
- p. Patient has a history of or acknowledges alcohol or substance abuse.
- q. Patient has a positive urine drug screen test result since the week 15 or week 16 visit of Study TV50717-CNS-30080 or at screening (as applicable) of this study (with exception of medications listed in [Table 11](#) of [Appendix H](#) or a justified medical explanation). Any request to include a patient with a positive urine drug screen test result should be discussed with, and approved by, the medical monitor.

## Statistical Considerations

### Sample Size Rationale:

This study is open-label and safety oriented in nature; therefore, no formal hypothesis testing is planned. The sample size for this study is not based on statistical considerations; hence, only descriptive statistics will be presented.

Based on the number of patients in the parent study (Study TEV50717-CNS-30080), approximately 45 patients who completed the parent study may enroll in this study.

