## AMENDMENT HISTORY

The protocol for Study TV50717-CNS-30081 (original protocol dated 07 March 2019) has been amended and reissued as follows:

Amendment 04	01 June 2022 42 patients enrolled to date
Administrative Letter 06	11 June 2021
Administrative Letter 05	23 February 2021
Administrative Letter 04	14 November 2020
Administrative Letter 03	14 July 2020
Amendment 03	23 June 2020 8 patients enrolled to date
Amendment 02	19 March 2020 3 patients enrolled to date
Amendment 01	02 October 2019 0 patients randomized/enrolled to date
Letter of Clarification 02	02 July 2019
Letter of Clarification 01	07 June 2019

The Summary of Changes to the Protocol includes the corresponding reason/justification for each change and is provided in Section [16](#).

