#### **Brief Summary of Study Design for the Trial Registry(s):**

Study TV50717-CNS-30081 is a 55-week study in which patients who have successfully completed the parent study (Study TV50717-CNS-30080) may be eligible to enroll in this study after they complete a 1-week period where no treatment is administered and the final evaluation at week 16. Patients may roll over from Study TV50717-CNS-30080 on the same day as the week 16 visit or up to 4 weeks from the week 15 visit of the TV50717-CNS 30080 study. Any

patient who cannot enroll within this timeframe, for any justified reason, must be discussed and pre-approved by the medical monitor prior to enrolling the patient. The end of Study TV50717-CNS-30081 is defined as the date of the week 55 follow-up telephone contact of the last participant.

This is an open-label study, and all patients who are enrolled will receive TEV-50717; there is no placebo treatment group. The purpose of the study is to determine whether long-term treatment with TEV-50717 is safe, tolerable, and effective in the treatment of dyskinetic involuntary movements associated with CP.

This study will include children and adolescents between 6 and 18 years of age at the time when they enrolled in the parent study (Study TV50717-CNS-30080). Informed consent/assent, as appropriate, based on the patient's age, will be obtained from the patient/parent/legally acceptable representative and caregiver (as applicable) at baseline/day 1 or screening visit (whichever comes first), and before any study procedures are performed. Informed consent/assent process can begin within 4 weeks before possible participation in the open-label study to allow patients adequate time to engage and ask questions.

Approximately 45 patients who have completed parent Study TV50717-CNS-30080 are planned for enrollment into this study.

Patients can either enroll in the study at the week 16 visit of Study TV50717-CNS-30080 or up to 4 weeks following the week 15 visit. The time when the patient enrolls (baseline/day 1) in this study will determine the assessments that will need to be performed at the initial visit for the study ([Figure 2](#)).

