#### 9.6. Safety Endpoints and Analysis

The primary objective of this study is to evaluate the safety and tolerability of long-term therapy with TEV-50717 in children and adolescents with DCP.

The safety measures/endpoints are as follows:

- adverse events
- vital signs
- children's C-SSRS
- ECG parameters
- clinical laboratory parameters (hematology, serum chemistry, and urinalysis)
- ESRS (subscale I and II)
- CBCL
- ESS

Safety analyses will be presented for the ITT analysis set (Section 9.2.1). Patients who did not receive any TEV-50717 will be excluded from the summaries and presented in listings only.

All adverse events will be coded using the Medical Dictionary for Regulatory Activities (MedDRA). Each patient will be counted only once in each preferred term or system organ class (SOC) category for the analyses of safety. Summaries will be presented for all adverse events (overall and by severity), adverse events determined by the investigator to be related to TEV-50717 (ie, reasonable possibility; see Section 7.1.4) (defined as related or with missing relationship) (overall and by severity), serious adverse events, and adverse events causing withdrawal from the study. Patient listings of serious adverse events and adverse events leading to withdrawal will be presented.

Observed values and changes from day 1 in laboratory results and vital signs will be summarized descriptively.

Observed values in ECG parameters will be summarized, and counts and percentages of abnormal findings will be presented. Changes from baseline of the parent study in ECG parameters will be summarized descriptively. In addition, the number and percentage of patients with on-treatment QTcF values >450, >480, or >500 msec and change from day 1 >30 or >60 msec will be presented.

The use of concomitant medications will be summarized by therapeutic class using descriptive statistics. Concomitant medications will include all medications taken while the patient is treated with TEV-50717.

The frequency and severity of suicidal ideation or behavior according to the children's C-SSRS questionnaire will be presented by visit. A shift table for children's C-SSRS categories at day 1, compared to the worst (highest) category during the treatment period, will be presented.

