Assessment of drug-induced parkinsonism according to the ESR (subscale I and II), assessment of change in behavior according to the CBCL questionnaire, and assessment of sedation according to the ESS questionnaire will be summarized descriptively.

Safety assessments and time points are provided in [Table 5](#).

For continuous variables, descriptive statistics will be provided for actual values and changes from day 1 to each time point. For categorical variables, patient counts and percentages will be provided. Descriptive summaries of serious adverse events, patient withdrawals due to adverse events, and potentially clinically significant abnormal values (clinical laboratory or vital signs) based on predefined criteria will be provided as well.

If any patient dies during the study, a listing of deaths will be provided and all relevant information will be discussed in the patient narrative included in the CSR.

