4. GENERAL ISSUES FOR DATA ANALYSIS

4.1. General

Descriptive statistics for continuous variables include number (n), mean, standard deviation (SD), standard error (SE), median, minimum, and maximum. Mean, SD and SE will not be presented if the number of patients in the analysis is less than 5 (n < 5).

Descriptive statistics for categorical variables include patient counts and percentages. Missing category will be displayed as appropriate.

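### The primary safety incidences are planned as counts and percentages with no measure of precision, and neither document says what rates about 45 patients can exclude.

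*Protocol*

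**What the plan says.** Protocol 9.6 sets the aim: "The primary objective of this study is to evaluate the safety and tolerability of long-term therapy with TEV-50717 in children and adolescents with DCP". The registry summary in the synopsis goes further: "The purpose of the study is to determine whether long-term treatment with TEV-50717 is safe, tolerable, and effective".

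The synopsis (Sample Size Rationale) gives the size, "approximately 45 patients who completed the parent study may enroll in this study", and the reasoning, "This study is open-label and safety oriented in nature; therefore, no formal hypothesis testing is planned" and "The sample size for this study is not based on statistical considerations; hence, only descriptive statistics will be presented". Protocol 9.1 and SAP 2.5 repeat it.

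On reporting, protocol 9.6 states "For categorical variables, patient counts and percentages will be provided" and SAP 4.1 states "Descriptive statistics for categorical variables include patient counts and percentages". For continuous variables, SAP 4.1 adds a standard deviation and a standard error to the mean (unless fewer than 5 patients contribute). Categorical variables get no counterpart. SAP 8.3 (adverse events), 8.9 (QTc prolongation) and 8.11 (C-SSRS) follow this pattern.

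Neither document plans a confidence interval for any safety rate or states the precision that the planned size allows. SAP section 9 has a Kaplan-Meier analysis of time to discontinuation, but only if more than 15% of patients withdraw, and it specifies no interval.

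**The concern.** The safety results that a reader will look at first are proportions in a small group. A percentage based on about 45 patients says little until one knows which true rates it still allows, and the planned tables do not show that. The word *hence* in the sample-size text links the absence of a sample-size calculation to presenting descriptive statistics only. That link gives no ground for leaving out precision. An interval around one observed proportion describes the data. It tests nothing, needs no target rate or margin, and is valid whatever fixed the sample size. What is at stake is how plainly the study can answer its own question on safety: a zero or a small count would be reported without the range of rates compatible with it.

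**Working it through.** The plan has no figure of its own to reproduce, because its size was not derived from an alpha, a power, a rate or a margin.

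**Inputs**
- n = 45, the planned enrolment (protocol synopsis, 9.1; SAP 2.5).
- n = 42 as a lower case: the amendment history of 1 June 2022 records "42 patients enrolled to date".
- Confidence level: not given in the documents. Assumption: 95%, two-sided, exact (Clopper-Pearson), with the one-sided 95% limit shown for zero events.
- C-SSRS denominator: only patients aged 12 or older (protocol 7.2.1; SAP 8.11). The number is not given. Assumption: 20 to 30.

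**Zero events.** The two-sided exact upper limit is 1 − 0.025^(1/n).
- n = 45: 1 − 0.025^(1/45) = 7.9%. The one-sided 95% version, 1 − 0.05^(1/45), is 6.4%.
- n = 42: 1 − 0.025^(1/42) = 8.4%.
- C-SSRS, n = 20: 1 − 0.025^(1/20) = 16.8%. With n = 30: 1 − 0.025^(1/30) = 11.6%.

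**One or more events.** For x of n, the lower limit is the 2.5% quantile of Beta(x, n − x + 1) and the upper limit is the 97.5% quantile of Beta(x + 1, n − x).

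| Events of 45 | Observed | Exact two-sided 95% limits |
|---|---|---|
| 0 | 0% | 0 to 7.9% |
| 1 | 2.2% | 0.06 to 11.8% |
| 2 | 4.4% | 0.5 to 15.1% |
| 5 | 11.1% | 3.7 to 24.1% |

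**Chance of seeing at least one case among 45**, 1 − (1 − p)^45:
- p = 1%: 1 − 0.636 = 36%
- p = 2%: 1 − 0.403 = 60%
- p = 5%: 1 − 0.099 = 90%

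A zero count is more likely than not only when (1 − p)^45 > 0.5, that is, when p < 1 − 0.5^(1/45), about 1.5%.

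**The case against.** The strongest reply is that nothing here is wrong. The study is openly descriptive, has no control arm and sets no rate to rule out. Counts with denominators let anyone compute an interval later, and protocol section 9 allows further analyses if the study report discloses them. The plan also offers more than incidence tables: event listings, narratives for deaths, an independent data monitoring committee, a C-SSRS shift table, exposure summaries, and changes from baseline with SD and SE. For rare serious events in a group this small, case review carries much of the weight. Finally, a binomial interval treats every patient as equally observed. Patients who stop early are not replaced, and only parent-study completers may enter.

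Most of this stands. It shows that the gap is not an error and that intervals would not complete the safety assessment. It does not show that precision is better left out. A list fixed in advance settles the outcomes and denominators before results are seen, which a later calculation by readers cannot do. The limits on follow-up and selection apply equally to the bare percentage, and should be stated beside the interval.

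Two stronger readings are tempting. A reader might infer that the plan treats a zero count as absence of risk, but no section says so. A reader might also infer that the plan declares anything beyond descriptive statistics impossible. The text says only what will be presented.

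**Conclusion.** The point holds as a recommended, inexpensive improvement to reporting. The descriptive design itself is not at fault. The primary safety incidences lack any measure of precision, and the stated reason does not justify that. On the two-sided exact 95% convention, no events among 45 patients is compatible with true rates up to 7.9% (8.4% at 42). That figure belongs to a zero count only: one event allows up to 11.8% and two up to 15.1%. It does not apply to the C-SSRS, where the limit for zero events is 11.6% to 16.8% if 30 to 20 patients are assessed, which is an assumption.

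A reader might go on to infer that zero is the likely result for the most serious outcomes. The documents do not support this. They give no expected rate in this population for the listed outcomes, and zero is the likelier result only for true rates below about 1.5%. The limits assume that every patient counts as fully observed. They do not reflect incomplete follow-up or the selection of parent-study completers.

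**What to change.** In SAP 4.1, 8.3, 8.9 and 8.11, add two-sided exact (Clopper-Pearson) 95% confidence intervals, labelled descriptive and unadjusted for multiplicity, for this fixed list:
- any serious adverse event;
- any treatment-emergent adverse event leading to discontinuation of drug or study;
- each QTcF criterion in SAP 8.9;
- any suicidal ideation or behaviour in the treatment period.

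Show the upper limit when the count is zero. Use treated patients as the denominator, which matches the exclusion of untreated patients from summaries in protocol 9.6. For the C-SSRS, use only assessed patients aged 12 or older, and print that number.

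In protocol 9.1 and SAP 2.5, add a sentence such as: with 45 treated patients, observing no event gives a two-sided exact 95% upper limit of 7.9%, and observing one event gives 11.8%. Add that the intervals do not account for incomplete follow-up or for enrolling only patients who completed the parent study.

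The cost is one column in a few tables and a short text change. SAP 2.6.2 provides for amendments approved before database lock. Sample size, data collection and the absence of hypothesis tests stay as they are. The downside is that the stated safety precision will look less favourable.
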